5.5. Accountability for Investigational Medicinal Product (IMP)

The Investigator is responsible for ensuring adequate accountability of all used and unused study drug. Accountability records (Study Drug Inventory Log) will be provided to each study site in order to:

- Record the date received and the quantity of study drug bottles.
- Record the date, subject number, subject initials, the study drug bottle number dispensed.
- Record the date, quantity of used and unused study drug returned by the subject, along with the initials of the person recording the information.

The Investigator [or designee (e.g., study center pharmacist) will acknowledge receipt of the study drugs from Gilead Sciences (or designee) after reviewing the shipment's content and condition. The Investigator (or designee) will be responsible for maintaining an accurate inventory of the dates and quantities of all study drugs received, dispensed, and returned. Subjects should be instructed to return all unused study drug to the site at their study visits.

Each dose of the study drug administered at the study center will be administered by qualified study center personnel. All doses of study drug administered to subjects in the clinic under the supervision of staff will be accurately recorded on the Study Drug Inventory Logs provided by Gilead Sciences (or on equivalent documentation maintained by the study center), which indicates the date and quantity of all doses of study drug dispensed to individual subjects. The requirements of all applicable drug dispensing laws will apply to all doses of study drugs dispensed by the Investigator (or designee).

The study drug inventory log must be available for inspection by the study monitor. Study drug supplies, including partially used or empty bottles, must be accounted for by the study monitor prior to destruction or return.

5.5.1. Study Drug Return or Disposal

The study monitor will provide instructions to the sites regarding the return of used and unused study drug. If return is not possible, the study monitor will evaluate each study center's study drug disposal procedures and provide appropriate instruction for destruction of unused study drug. If the site has an appropriate standard operating procedure (SOP) for drug destruction as determined by Gilead QA, the site may destroy used (empty or partially empty) and unused study drug bottles in accordance with that site's approved SOP. A copy of the site's approved SOP will be obtained for central files.

If the study drug is destroyed on site, the investigator must maintain accurate records for all study drug destroyed. Records must show the identification and quantity of each unit destroyed, the method of destruction, and the person who disposed of the study drug. Upon study completion, copies of the study drug accountability records must be filed at the site. Another copy will be returned to Gilead. The study monitor will review study drug inventory and associated records at periodic intervals.

6. STUDY PROCEDURES

The study procedures to be conducted for each subject enrolled in the study are presented in tabular form in [Appendix 2](#) and described in the text that follows.

The investigator must document any deviation from protocol procedures in the subject's source documents and electronic Case Report Forms (eCRFs). In addition, the Sponsor and the Contract Research Organization (CRO) should be promptly notified of any protocol deviations.

6.1. Subject Enrollment and Treatment Assignment

It is the responsibility of the investigator to ensure that each subject is eligible for the study before enrollment. Please refer to Section [5.1](#) for details about enrollment and treatment assignment.

6.2. Pretreatment Assessments

6.2.1. Screening Visit

Subjects will be screened within 30 days before Day 1 Visit to determine eligibility for participation in the study. The following will be performed and documented at screening:

- Obtain written informed consent
- Obtain medical history including history of HIV-1 disease-related events, substance use, family history of cardiovascular disease (i.e. myocardial infarction, stroke, peripheral vascular/arterial disease, and/or angina) and prior medications within 30 days of the Screening Visit
- Complete physical examination (urogenital/anorectal exams will be performed at the discretion of the Investigator)
- Vital signs measurement (blood pressure, pulse, respiration rate and temperature) and weight
- 12-lead ECG performed supine
- Height
- Blood sample collection for the following laboratory analyses:
 - Serum pregnancy test (females of childbearing potential only). If the test is positive, the subject will not be enrolled.
 - FSH test is required for female subjects who have stopped menstruating for > 12 months but do not have documentation of ovarian hormonal failure.

- Chemistry profile: alkaline phosphatase, AST, ALT, GGT, total bilirubin, direct and indirect bilirubin, total protein, albumin, LDH, CPK, bicarbonate, BUN, calcium, chloride, creatinine, glucose, phosphorus, magnesium, potassium, sodium, uric acid, PT/INR, amylase (reflex lipase testing is performed in subjects with total amylase $> 1.5 \times \text{ULN}$) and parathyroid hormone (PTH)
 - Sample should be drawn prior to hemodialysis
 - Timing of draw and timing of hemodialysis should be recorded
- Estimated GFR according to the Cockcroft-Gault formula for creatinine clearance:

Male:
$$\frac{(140 - \text{age in years}) \times (\text{wt in kg})}{72 \times (\text{serum creatinine in mg/dL})} = \text{CL}_{\text{cr}} \text{ (mL/min)}$$

Female:
$$\frac{(140 - \text{age in years}) \times (\text{wt in kg}) \times 0.85}{72 \times (\text{serum creatinine in mg/dL})} = \text{CL}_{\text{cr}} \text{ (mL/min)}$$
- Hematology profile: complete blood count (CBC) with differential and platelet count
- CD4+ T cell count
- Plasma HIV-1 RNA (Taqman v2.0)
- Hepatitis B virus surface antigen serology (HBsAg)
- Hepatitis C virus (HCVAb) serology. If the antibody test result is positive, HCV RNA test will be performed to confirm HCV viremia.
- HIV-TSQs (HIV Treatment Satisfaction Questionnaire Status) should be completed by the subject. Subject is to read the questionnaire by him/herself and write/mark answers directly onto the questionnaire.
- Review of AEs and concomitant medications (adverse events related to protocol mandated procedures occurring after signing of the consent form)

Subjects meeting all of the inclusion criteria and none of the exclusion criteria will return to the clinic within 30 days after screening for Day 1 assessments.

From the time of obtaining informed consent through the first administration of study drug, record all serious adverse events (SAEs), as well as any adverse events related to protocol-mandated procedures on the adverse events case report form (eCRF). All other untoward medical occurrences observed during the screening period, including exacerbation or changes in medical history are to be captured on the medical history eCRF. See Section 7 Adverse Events and Toxicity Management for additional details.

6.2.2. Day 1 Assessments

The following evaluations are to be completed after confirmation of eligibility, and before the study drug is dispensed to the subject. Initiation of treatment with the study drug must take place within 24 hours after the Day 1 Visit.

- Obtain subject number and study drug bottle assignment from IWRS. The subject number assignment and enrollment may be performed up to 3 days prior to the in-clinic Day 1 Visit provided that all screening procedures have been completed and subject eligibility has been confirmed.
- Review of AEs and changes in concomitant medications
- Complete physical examination (urogenital/anorectal exams will be performed at the discretion of the Investigator)
- Vital signs (blood pressure, pulse, respiration rate, and temperature) and weight
- Blood sample collection for the following laboratory analyses:
 - Chemistry profile: alkaline phosphatase, AST, ALT, GGT, total bilirubin, direct and indirect bilirubin, total protein, albumin, LDH, CPK, bicarbonate, BUN, calcium, chloride, creatinine, phosphorus, magnesium, potassium, sodium, uric acid, amylase (reflex lipase testing is performed in subjects with total amylase $> 1.5 \times$ ULN) and PTH
 - Sample should be drawn prior to hemodialysis
 - Timing of draw and timing of hemodialysis should be recorded
 - Metabolic assessments: Fasting (no food or drinks, except water, at least 8 hours prior to blood collection) glucose and lipid panel (total cholesterol, HDL, direct LDL, and triglycerides). If the subject has not fasted prior to the visit, the visit may proceed, but the subject must return within 72 hours in a fasted state to draw blood for the metabolic assessments
 - Estimated glomerular filtration rate according to the Cockcroft-Gault formula for creatinine clearance
 - Hematology profile: complete blood count (CBC) with differential and platelet count
 - Plasma HIV-1 RNA (Taqman v2.0)
 - CD4+ T cell count
 - Whole blood storage sample collection for virology analyses
 - Plasma storage sample for virology, safety and/or PK testing

- Serum and plasma storage samples for possible additional clinical testing (for subjects who provide consent)
- Serum pregnancy test (females of childbearing potential only)
- SF-36, VAS and HIV-TSQs should be completed by the subject. Subject is to read the questionnaire by him/herself and write/mark answers directly onto the questionnaire.
- Site-administered questions for Health Utilization Assessment to be completed
- Study drug dispensation. Study drug will be dispensed in an open-label fashion. Subjects must initiate dosing of study drug on the day of the Day 1 Visit.
- Subjects should be instructed to take E/C/F/TAF FDC tablets once daily with food at the same time each day. On the days of hemodialysis, subjects should be instructed to take study drug after completion of hemodialysis. Subjects should also be counseled regarding the importance of adherence and taking their study drugs at approximately the same time each day.

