5. INVESTIGATIONAL MEDICINAL PRODUCTS

5.1. Enrollment

This is an open-label, single arm study. All eligible subjects will receive open-label E/C/F/TAF. Enrollment and Day 1 Visit cannot occur until subject eligibility has been confirmed.

It is the responsibility of the Investigator to ensure that the subject is eligible for the study prior to enrollment. Once eligibility is confirmed, each subject will be assigned a unique subject number using Interactive Web Response System (IWRS). Once a subject number has been assigned to a subject, it will not be reassigned to any other subject. The subject number assignment may be performed up to 3 days prior to the in-clinic Day 1 Visit, provided that all other screening procedures have been completed and subject eligibility has been confirmed.

Eligibility must be confirmed and all Day 1 tests and procedures must be completed prior to the administration of the first dose of study drug.

IWRS will assign study drug bottle numbers at each study visit. Initiation of study drug must take place on the day of Day 1 Visit.

Post-Week 96

At the End of E/C/F/TAF Visit, the IWRS will assign open-label B/F/TAF FDC.

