3.8. Analysis Windows

3.8.1. Definition of Study Day

Study Day 1 is defined as the day when the first dose of E/C/F/TAF study drug was taken, as recorded on the Study Drug Administration eCRF form.

B/F/TAF Study Day 1 is defined as the day when the first dose of B/F/TAF study drug was taken, as recorded on the Study Drug Administration eCRF form.

Study Days are calculated relative to Study Day 1 and B/F/TAF Study Day 1. For events that occurred on or after Study Day 1, study days are calculated as (visit date minus Study Day 1 plus 1). For events that occurred prior to Study Day 1, study days are calculated as (visit date minus Study Day 1).

E/C/F/TAF Last Dose Date is the latest of E/C/F/TAF study drug end dates recorded on the Study Drug Administration eCRF form with “Permanently Withdrawn” box checked for subjects who prematurely discontinued study drug or who completed study drug according to the Study Drug Completion eCRF.

If the date of E/C/F/TAF last dose is missing (eg, only year of last dose is known or completely missing due to lost to follow-up) for subjects who prematurely discontinued or completed study drug, the latest of the E/C/F/TAF study drug start dates and end dates, the clinic visit dates, and the laboratory visit dates, excluding the date of the 30-day follow-up visit and any dates on or after the first dose of B/F/TAF if applicable, will be used to impute the last dose date. For other partial missing last dose dates, please see programming specifications ([Appendix 7](#)) for imputation rule details.

B/F/TAF Last Dose Date is the latest of B/F/TAF study drug end dates recorded on the Study Drug Administration eCRF form with “Permanently Withdrawn” box checked for subjects who prematurely discontinued study drug or who completed study drug according to the Study Drug Completion eCRF.

If the date of B/F/TAF last dose is missing (eg, only year of last dose is known or completely missing due to lost to follow-up) for subjects who prematurely discontinued or completed study drug, the latest of the B/F/TAF study drug start dates and end dates, the clinic visit dates, and the laboratory visit dates, excluding the date of the 30-day follow-up visit and any dates before the first dose of B/F/TAF, will be used to impute the last dose date. For other partial missing last dose dates, please see programming specifications ([Appendix 7](#)) for imputation rule details.

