Last Study Date is the latest of E/C/F/TAF or B/F/TAF study drug start date and end date, clinic visit dates, and laboratory visit dates, including the 30-day follow-up visit date, for subjects who prematurely discontinued the study or who completed the study according to Study Completion eCRF.

Baseline value for the E/C/F/TAF phase is defined as the last value obtained on or prior to Study Day 1 for all assessments. Baseline value for the B/F/TAF OL extension phase is defined as the last value obtained on or prior to B/F/TAF Study Day 1 for all assessments.

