8.4.2.1. Treatment-Emergent Laboratory Abnormalities

E/C/F/TAF treatment-emergent laboratory abnormalities are defined as values that increase at least 1 toxicity grade from baseline at any postbaseline time point up to 30 days after the permanent discontinuation of E/C/F/TAF study drug for subjects who do not participate in the B/F/TAF OL extension phase or up to the date of the first B/F/TAF study drug dose for subjects who participate in the B/F/TAF OL extension phase.

B/F/TAF treatment-emergent laboratory abnormalities are defined as values that increase at least 1 toxicity grade from baseline at any postbaseline time point up to 30 days after the permanent discontinuation of B/F/TAF study drug.

If the relevant baseline laboratory value is missing, any abnormality of at least Grade 1 observed within the time frame specified above will be considered treatment-emergent.

Fasting glucose and nonfasting glucose (including glucose result without a known fasting status) are graded based on different grading scales as specified in the protocol. Treatment-emergent laboratory abnormalities will be summarized for fasting glucose. Maximum postbaseline grade, instead of treatment-emergent grade, for nonfasting glucose will be summarized, as nonfasting glucose was not assessed at baseline visit for most of the subjects; therefore, whether an abnormality is treatment-emergent or not cannot be determined for these subjects.

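### A fasting lipid redraw taken after the first dose cannot serve as baseline, so a pre-existing lipid abnormality can be reported as treatment-emergent

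*Protocol*

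**What the plan says.** **Timing of the draw and of dosing.** Protocol 6.2.2 allows an unfasted Day 1 visit to go ahead: "If the subject has not fasted prior to the visit, the visit may proceed, but the subject must return within 72 hours in a fasted" condition for the glucose and lipid draw. On dosing, the same section says two things. Its opening paragraph has "Initiation of treatment with the study drug must take place within 24 hours after the Day 1 Visit", repeated in note b of Appendix 2. Its dispensing item has "Subjects must initiate dosing of study drug on the day of the Day 1 Visit", and Protocol 5.1 agrees with that. Protocol 5.1 also requires that "all Day 1 tests and procedures must be completed prior to the administration of the first dose of study drug", and the opening of 6.2.2 places the Day 1 evaluations before drug is dispensed.

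**Baseline.** SAP 3.8.1 ties the study-day clock to dosing, not to the visit: "Study Day 1 is defined as the day when the first dose of E/C/F/TAF study drug was taken". It continues: "Baseline value for the E/C/F/TAF phase is defined as the last value obtained on or prior to Study Day 1 for all assessments". There is no exception for fasting tests. Table 3-2 ends Baseline at Day 1 and runs the Week 24 window from Day 2 to Day 252.

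**Missing baseline.** SAP 8.4.2.1: "If the relevant baseline laboratory value is missing, any abnormality of at least Grade 1 observed within the time frame specified above will be considered" to have emerged on treatment. Protocol 8.5.3 has the same convention. SAP 8.4.2 leaves nonfasting lipids ungraded. SAP Appendix 7, item 14, brings every graded postbaseline result into the toxicity summary, whether or not it belongs to a summarized visit.

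**The concern.** The protocol gives an unfasted subject a way to supply a fasting sample, but the SAP may be unable to use that sample as baseline. When the redraw comes after the first dose, a lipid abnormality that was there before the switch is counted as emerging on E/C/F/TAF, and the redraw itself can be the record that triggers the count. The same subject also has no change from baseline, no place in the lipid shift table by baseline category, and no place in the Week 96 lipid sensitivity analysis (SAP 8.4.3), which needs both values.

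The grading error runs in one direction only, and a single-arm study has no comparator in which it would also appear.

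**Working it through.** The plan gives no figure of its own here, so the check is date arithmetic followed by a rough size.

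**1. Is there an earlier fasting sample?** Protocol 6.2.1 lists no lipids at Screening, Protocol Appendix 2 has no Screening mark for metabolic assessments, and SAP 1.2 starts fasting lipids and glucose at Day 1. The protocol synopsis differs, naming Screening as well. Under the detailed schedule there is no fallback for lipids. Glucose is in the Screening chemistry profile, so a Screening sample that happened to be fasted would qualify as the glucose baseline.

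**2. Where does the redraw land?** SAP 3.8.1: study day = date − Study Day 1 + 1 on or after the first dose, and date − Study Day 1 before it. The 72-hour limit is taken as up to 3 calendar days after the visit.

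| Redraw, days after visit | First dose on visit day | First dose next day |
|---|---|---|
| 0 | Day 1: baseline | Day −1: baseline |
| 1 | 1 − 0 + 1 = Day 2: postbaseline | 1 − 1 + 1 = Day 1: baseline |
| 2 | Day 3: postbaseline | Day 2: postbaseline |
| 3 | Day 4: postbaseline | Day 3: postbaseline |

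Five of the eight combinations lose the baseline. If all Day 1 tests do precede dosing, none does.

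**3. What follows for a postbaseline redraw?** With no gradable fasting value by Study Day 1, the missing-baseline rule applies. Protocol Appendix 6 starts grading at 130 mg/dL for adult fasting LDL (Grade 1), 200 mg/dL for fasting total cholesterol (Grade 1) and 500 mg/dL for fasting triglycerides (Grade 2, as there is no Grade 1). Fasting glucose starts at 110 mg/dL (Grade 1). HDL has no grade, so for HDL only the baseline is lost.

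In by-visit tables SAP 3.8.3 picks the record closest to Day 168, so a Day 2 to 4 redraw would stand for Week 24 only if no other fasting record fell in Days 2 to 252.

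**4. Size.** The E/C/F/TAF Safety Analysis Set has 55 subjects (SAP Appendix Table 1). One subject is 1/55 = 1.8 percentage points, or slightly more, because SAP 8.4.2.2 divides by subjects with a postbaseline value. The documents give neither the number unfasted on Day 1 nor the prevalence of earlier abnormalities. For illustration only, assume 5% to 20% end up without a fasting baseline and 10% to 50% of those have a pre-existing graded value for a given test:

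- without baseline: 0.05 × 55 = 2.75 to 0.20 × 55 = 11 subjects
- misclassified per test: 2.75 × 0.10 = 0.3 to 11 × 0.50 = 5.5 subjects
- as a share: 0.05 × 0.10 = 0.5% to 0.20 × 0.50 = 10%

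**The case against.** The strongest reply is that the protocol already prevents this. Section 5.1 puts all Day 1 tests before the first dose, and SAP Study Day 1 follows the dose rather than the visit, so a compliant redraw would always be a valid baseline. That stands as one reading. But the same protocol requires dosing on the visit day or within 24 hours, and neither rule waits for a 72-hour return. A site cannot use the full allowance and keep all of these rules.

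Second, counting abnormalities when baseline is missing is a deliberate cautious convention, prespecified in both documents, and no formal testing depends on it. True; the convention itself is not at fault. The difficulty is that a fasting value close to baseline exists and is used as evidence of emergence.

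Third, a baseline taken on treatment is not a clean one. Protocol 1.2.5 reports fasting lipid increases on E/C/F/TAF in treatment-naive studies at Week 48, and the documents say nothing about changes over the first few days. This stands as a cost of the remedy. So does consistency: SAP 2.2 to 2.4 state that the Week 24, 48 and 96 analyses are already done.

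A reader might go further and infer that every unfasted subject loses the baseline, or that the redraw is thrown away. The documents do not support either inference: a redraw on or before the day of first dose remains baseline, and a later one is kept as a postbaseline record.

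**Conclusion.** The point holds conditionally. When the redraw falls on a calendar day after the first dose, the plan as written leaves the fasting lipid baseline missing and can report a pre-existing LDL, total cholesterol or triglyceride abnormality as treatment-emergent. For fasting glucose this needs the further condition that no fasted Screening glucose exists. It assumes the detailed schedule, rather than the synopsis, governs Screening.

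The number affected is unknown and probably small. SAP 8.4.2.1 remarks that most subjects had no nonfasting glucose at the baseline visit, which points that way, though weakly, since Day 1 chemistry omits glucose by design. The 5% to 20% and 10% to 50% ranges are assumptions, not estimates.

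A reader might infer a material upward bias in the study's safety result. That is not supported: the effect is confined to fasting metabolic laboratory summaries. The primary endpoint (Grade 3 or higher adverse events) and the virologic endpoints do not use these baselines. In the B/F/TAF phase, fasting values from the earlier phase can serve as baseline, so the gap is largely an E/C/F/TAF one.

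**What to change.** In SAP 3.8.1 and Table 3-2, add a rule for fasting glucose and lipids only. When no fasting value exists on or before Study Day 1, take as baseline the fasted redraw that the protocol permits (within 72 hours of the Day 1 visit, at latest Study Day 4), and do not also count it as a postbaseline record. A fasted Screening glucose, where there is one, stays the glucose baseline under the existing rule.

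Flag these subjects in the listing, show the fasting metabolic summaries with and without them, and record the difference from the interim analyses in the final report, as SAP Section 1 already provides for later changes.

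The cost is one sentence, one table note and one extra set of summaries. The statistical downside is that a few baselines follow up to about three doses, so any very early drug effect would be absorbed into them; the with-and-without display shows whether that matters.

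Protocol 5.1 and the statements within 6.2.2 on testing, dispensing and dosing must be reconciled with the 72-hour allowance, and the synopsis with the detailed schedule on fasting tests at Screening. Which timing rule should prevail is not for this review to say.
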